All subjects who participate in PGT-SC genetic testing will receive a telephone call two weeks after results are mailed, to assess PGT-SC result comprehension and potential distress (see Two Week Risk Feedback Comprehension Assessment) and to answer any questions they may have. All those who

complete this Assessment will receive a \$5 Target Gift card as thanks for their effort. Based on prior literature documenting low levels of distress in those undergoing genetic testing for high-risk mutations, and among those found to carry *CDKN2A* mutations, we anticipate low levels of distress regarding PGT-SC feedback. Anyone who reports high distress will be referred to Clinic Director and Co-Investigator [name], who addresses distress issues regularly in the UNM clinic. If they wish, a genetic counselor will be available.

E) Three-month follow-up.

All participants who completed Baseline Assessments (whether tested or not) will be contacted for assessment by telephone three months after PGT-SC testing (Three Month Follow Up Questionnaire). Participants who complete this three-month follow up assessment will receive a \$15 Target Gift card for their valued study participation.

F) Group 1 genetic testing option.

Those 120 participants randomized to the control group will receive an offer for PGT-SC directly after the three-month follow-up assessments. They will be offered testing, and of those who pursue testing, will receive results by mail or by email, sent by the PA who enrolled them, and a two-week follow-up telephone call to assess result comprehension and potential distress.

G) Summary.

We anticipate that patients will be enrolled over an approximately 12 month period, complete assessments and receive feedback within 20 months. Thus individuals are estimated to be in the study for 3 months and the enrollment and assessment period overall will last as long as 20 months total. Primary analyses will be completed in the 6 months following the 24 months period of participation; the entire study will take 3 years.

9) Study Endpoints.

Primary endpoints are based on the 3-month follow up questionnaires. The primary study endpoints include personal utility of Personal Genomic Testing for Skin Cancer (PGT-SC) in terms of short-term (three months after testing) sun protection, skin screening (i.e., behaviors), communication, melanoma threat and control beliefs (i.e., putative mediators of behavior change), as well as differential reach of PGT-SC across Hispanics and non-Hispanics, as well as potential explanations for any differential reach. These will include the construct/measures listed below:

Construct/Measure	Prior work/psychometrics	Assess point
Sun protection and skin screening (Sunscreen, shade seeking, clothing and hat usage) on separate 5-point scales (never-always); health provider screening (no/yes).	Item reliability $\geq 80\%$. (Ganz, 2008)	B, 3-month
Family/physician communication. Frequency, content of communication with physicians, family, and friends regarding skin cancer risk, interest in genetic information; 4-point scales (not at all-a lot).	Items used with high comprehensibility in population-based studies ([name] 2005, 2009, 2012, 2014)	B, 3-month, (interest in genetic information only)

Perceived skin cancer threat belief (Witte 1996). Includes assessment of risk perceptions (verbal, percent likelihood, comparison) on separate scales (5 to 10-point) from low-high, with “don’t know” option (Waters 2013); worry, assessed with 4-point items (never-all the time). Perceived skin cancer control beliefs (Witte 1996) Includes skin cancer prevention self-efficacy (7 items, on separate 4-point scales; not at all-extremely capable), skin cancer prevention response-efficacy (7 items, on separate 4-point scales; not at all to extremely important).
	
Widely used perceived risk items drawn from prior health behavior research (Weinstein 1982), Lerman’s cancer worry scale (Lerman 1991), and perceived cancer severity (Aiken 1994). Control belief items (Bandura 1986) predicting uptake of cancer prevention behaviors; adapted for skin cancer prevention ([name] 2006).
	
B, 3-month (risk perception question only)

Hispanic ethnicity
	
For initial sampling frame (50%) Hispanic, self-report as per Baseline survey.
	
B


Health Literacy includes 3 items: level of confidence in filling out medical forms independently, frequency of needed assistance reading hospital materials, and frequency of problems learning about medical conditions because of difficulty reading hospital materials (5-point scales, none of the time-all the time).
	
Single Item Literacy Screener Items (Chew 2004, 2008) are feasible in primary care populations, with more limited respondent burden compared to TOFHLA or REALM; Area under Receiver Operating Characteristic Curve analyses indicate good sensitivity for diverse literacy levels.
	
B

Health System Distrust includes 9 items assessing two domains; values and competence distrust in 5-point scales (strongly agree-strongly disagree).
	
The Health System Distrust Scale (Shea 2008) is validated in primary care against established physician trust scales; reliability overall (0.83), Values (0.73); Competence (0.77).
	
B

Sociocultural factors includes a 15-item assessment of Cancer Fatalism on 2-point scales (agree/disagree), a 4-item assessment of Family Health Orientation: social influences on learning more about health, social influences on doing more about health, how motivated they are to do what important others want them to do, how much their health choices affect others (7-point scales, strongly disagree- strongly agree), and 10-item assessing Skin Cancer Misconceptions, including
	
Cancer Fatalism predicts cancer prevention activities (Espinosa de Los Monteros, 2011); we use Powe Cancer Fatalism Scale (Powe 1995) examining fear, pessimism, death inevitability, and predetermination beliefs. It is well validated (Espinosa de Los Monteros, 2011), and reliable (.88). Family Health Orientation assessed via social influences on health information seeking and behavior change from Multiplex ([name] 2012), and
	
B

preventability, treatability, and information overload about skin cancer (Agree/Disagree).	Skin Cancer Misconceptions items from the Health Information National Trends Survey 2007 (NCI, 2007) and found to be lower among Hispanics (Torres 2014).	
Knowledge and satisfaction with PGT-SC invitation modules, all on 7-point scales (strongly disagree-strongly agree; see Appendix I for items).	Adopted from the NHGRI Multiplex Study (Kaphingst 2010).	Embedded in PGT-SC invitation (Appendix I)
Test result comprehension includes recall, perceived clarity, interpretation and recall, believability, and test regret on closed, open-ended scales.	Adopted from the NHGRI Multiplex Study (Kaphingst 2012, McBride 2009).	Risk feedback comp. assessment
Cancer-related Distress is assessed through 7 items on separate 5-point scales (not at all-extremely).	Impact of Events Scale – Revised Intrusive thoughts subscale (Horowitz 1979) is widely used with good internal and test-retest reliability; good ability to distinguish those with cancer distress (Joseph 2000; Thewes 2001).	Risk feedback comp. assessment; 3-month
Demographics (birth year, US nativity, survey language choice, gender, education, income, race/ethnicity); Internet availability.	Standard demographic questions; Internet availability (Nelson 2004).	B
Melanoma risk factors (personal and family melanoma history; phenotype, sunburn hx).	Heavily used items from prior epidemiology research (Gandini 2005).	B

References for Endpoints:

Bandura A. *Social foundations of thought and action: a social cognitive theory*. Englewood Cliffs, NJ: Prentice-Hall; 1986.

Espinosa de Los Monteros K, Gallo LC. The relevance of fatalism in the study of Latinas' cancer screening behavior: a systematic review of the literature. *International journal of behavioral medicine*. Dec 2011;18(4):310-318.

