In Phase II, patients will be eligible for the study if they have been registered at a UNM Clinic for six months and assigned a primary care provider, aged >18, and are fluent in either English or Spanish. We will exclude adults that are unable to consent, individuals who are not yet adults (infants, children, teenagers) and prisoners. Pregnant women will be eligible to participate. All participants in Phase II will be consented and interviewed at 1209 University Clinic, OSIS Orthopedic Clinic at [name], the Family Medicine Clinic, the Center for Employee and Occupational Health Services, both at [name] or the North Valley Clinic. Individuals who usually attend another UNM Clinic (Atrisco Heritage Center for Family and Community Health, Northeast Heights Clinic, North Valley Clinic, Westside Clinic, Southeast Heights Center for Family and Community Health, Family Medical Center, Lobo Care Clinic, Senior Health Center, or Southwest Mesa Center for Family and Community Health) and are accompanying a patient from these Clinics will be eligible for Phase II.

6) Number of Subjects (Recruitment Target)

Phase 1: We anticipate that we will conduct cognitive interviews of **40** subjects fluent in Spanish, 20 men and 20 women, who either completed high school or did not complete high school (see phase I recruitment table).

Phase I Recruitment Table

Gender

Education	Male	Female
Completed high school/equivalent or greater	10	10
Did not complete high school or equivalent	10	10

Usability Phase: We will conduct the usability survey in **up to 10** subjects who attend the 1209 Clinic.

Phase II: We anticipate that we will conduct a baseline assessment of **650** subjects (see SOMBRA Study Flow, p. 6). They will then be randomized to a “Wait List Control Group of **120** subjects and a PGT-SC group of **530** subjects. All **530** subjects will be offered MC1R genetic testing. The “Wait List Control Group (**120** subjects) will be offered the MC1R test after the **Three Month Follow Up Questionnaire**. Accordingly, all **650** subjects will be offered MC1R testing. Of those offered, based on our prior experience, we anticipate 30-50 percent will accept an invitation for testing.

Phase II: Recruitment Tables	Ethnicity	
	Hispanic	NHW
Waitlist Controls – n = 120	60	60
PGT-SC Group – n=530	265	265

7) Recruitment Methods

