C) Baseline Assessment. All participants approached will be asked to complete a three minute Eligibility Screening and a Screening Survey to determine their interest in and eligibility for study participation, as well as basic demographics. If they are eligible and interested in study participation, the PA will fully explain the study and the participant will provide written informed consent (Consent - Number 2 and UNMHSC_HIPAA_Authorization), receiving a copy of the signed consent form. The PA will guide them to complete the Baseline Questionnaire in the clinic in a semi-private space with dedicated study computer (tablet or laptop computer).

Based on prior research, we anticipate that 30% of those approached will participate and complete the Baseline Questionnaire. Sample size estimates indicate that a total number of participants of 885 is necessary to evaluate our outcomes.

After completion of the Baseline Questionnaire facilitated by the PA, participants will receive a \$15 Target Gift card for their time and effort. They will sign a Sombra Gift Card Form and receive a Sombra Appointment Card. They will then be randomized to Group 1 - wait-list controls or to Group 2 to consider PGT-SC through a secure website (randomized and balanced across Hispanic and Non-Hispanic ethnicity, n=120 in control arm, n=530 in PGT-SC arm). "Hispanic" ethnicity will be recorded by self-report. Patients will choose Spanish or English study materials.

D) PGT-SC Invitation. (Group 2 – n=530)

Participants randomized to the PGT-SC study arm will view materials on the SOMBRA Website via Internet from a home, work, library or community-based organization computer, or alternatively through a paper version of the modules if they prefer. Internet reach in Albuquerque is >80% and WiFi is available throughout the city. All participants will be asked to consider the four educational modules regarding PGT-SC. The PGT-SC modules are:

- 1) What genetic testing can and cannot tell you,
- 2) Skin cancer and genes,
- 3) Your rights if you take part in genetic research, and
- 4) Your decision to be tested or not.

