After each module, participants will be asked to answer a series of questions regarding knowledge and satisfaction with the content of each module, and after section 4 they will be asked to register a decision as to whether they wish to have a skin cancer genetic test, or not. Participants will only be able to register a test decision if they have already read and completed the questions on the first three educational modules. Knowledge and satisfaction questions are part of each module. Those who complete these steps will receive an additional \$5 target Gift card incentive for each module for a maximum a total of \$15 in Target Gift card incentives. There is no incentive associated with the 4th module on the decision to conduct genetic testing or not.

Registration of a test decision (yes; no) is our primary assessment of "reach" in this study. We expect a minimum of 30% of participants who complete the Baseline Survey to register a genetic test decision, and that this will reach 50% in some subgroups, including those with higher literacy. Additional assessments of "reach" include completion of the baseline survey and decision to pursue PGT-SC testing (yes; no).

Those who register a decision to proceed with testing will receive a DNA buccal cell test kit with instructions (Donor Mailing Form and Specimen Collection Form), which will allow them to provide a saliva sample for genetic testing, pre-paid postage envelope, and instructions in English and Spanish for buccal cell collection. Based on The Multiplex Study, we anticipate that up to 50% of participants who consider PGT-SC will return a saliva sample for genetic testing. The Molecular Epidemiology Laboratory at UNM HSC will conduct testing; participants will receive PGT-SC results by mail (or by email, if they prefer) within one month.

We will employ state-of-the-art methods of risk communication used with high comprehension in the Multiplex Study, guided by Co-Investigator [name], who originally developed Multiplex Study risk communication materials. These materials combine verbal and pictorial displays of risk information and denominator information. We will also provide written information to clarify risk level given that individuals tend to rely on the gist of the information provided (See SOMBRA Result A for average risk individuals and SOMBRA Result B for higher risk individuals)

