We will share results of genetic testing with individual study participants (SOMBRA Result A – average risk results, and SOMBRA Result B – increased risk results). The results are **not actionable, but informational**. The PA will mail results to the study participant as was done in the Multiplex Study, or if the participant wishes – by email. If there are any signs of distress in any way, we will work with [name], the Director of the Clinic, and with [name], a cancer genetic counselor at the UNM Cancer Center, as necessary. Additionally, we will be assessing distress levels two weeks after the PGT-SC results have been received, and at all follow-up time points. Through the ongoing monitoring process of the study (e.g., regular meetings with research staff), the PIs and Co-Investigators will be informed of any concerns/distress that occur among study participants.

22) **Resources Available**

Qualifications of Investigators: [name] has been conducting epidemiologic research internationally and locally for the past 27 years. Her CV is attached. [name] has been conducting psychological and behavioral research for more than 15 years. Her CV is attached.

Project Assistants will interview individuals who agree. They are bi-lingual in English and Spanish, with either a Bachelor's degree and at least two years' experience that is applicable to the duties listed in the job description, or a Master's degree with at least six

months' experience that can be demonstrated to be applicable to the duties listed in the job description.

Recruitment plan/access to potential recruits. [name], Director of the 1209 UNM Primary Care Clinic, is a co-investigator and will assist the study with logistics at the Clinic and in working with the Clinic staff. Previously, we conducted a pilot study of 100 patients at the clinic with positive results and no negative feedback.

We will post a flyer (Clinic Flyer) explaining the study to the population of individuals attending the Clinic. In the pilot study, we recruited 100 patients in 3 days; therefore, our plan to spend several months to recruit 885 patients seems quite feasible. We will meet with the staff at the clinic to explain our goals. There are quiet spots within the clinic where we can easily discuss the study with interested individuals, explain Informed Consent and HIPAA and conduct the Baseline Questionnaire.

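### The protocol calls a Phase II total of 885 necessary but allocates 650; the text gives no step from one to the other and no calculation behind either

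*Combined protocol and SAP*

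**What the plan says.** Two totals for Phase II stand in the current text of the protocol.

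**885.** Section 8C (Baseline Assessment) states: "Sample size estimates indicate that a total number of participants of 885 is necessary to evaluate our outcomes". Section 22 (Resources Available) argues from the pace of a pilot study that "our plan to spend several months to recruit 885 patients seems quite feasible".

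**650.** Section 6 (Number of Subjects) plans a baseline assessment of 650, followed by randomisation of 120 to the wait list and 530 to PGT-SC. Its table splits these as 60 + 60 and 265 + 265 by ethnicity, and the text adds: "Accordingly, all 650 subjects will be offered MC1R testing". The paragraph of section 8C after the 885 describes allocation as "randomized and balanced across Hispanic and Non-Hispanic ethnicity, n=120 in control arm, n=530 in PGT-SC arm". Section 8D repeats the 530 and section 8F the 120.

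The sentence directly before the 885 gives a participation rate: "we anticipate that 30% of those approached will participate and complete the Baseline Questionnaire". Section 13 allows for up to 20% being unreachable at three months. Neither rate is presented as a bridge between the totals. No significance level, power, effect size, standard deviation or target comparison is given for either one.

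**The concern.** The 885 is the protocol's only claim about the size it needs, and the allocation plan does not match it. If 885 is a leftover, the arm sizes in use have no stated basis. If 885 is current, the arm sizes and the recruitment table are wrong. In both cases a reader cannot tell what the trial was sized to detect, either for the Aim I outcomes by randomised arm or for reach by ethnicity, both of which section 9 places among the primary endpoints.

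**Working it through.** **Inputs**
- 885: sections 8C and 22.
- Arms of 120 and 530: sections 6, 8C, 8D and 8F. Ethnic split 60/60 and 265/265: section 6 table.
- Participation 30% of those approached: section 8C.
- Loss at three months up to 20%: section 13.
- Alpha, sidedness, power, effect size, SD: not stated.

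**1. The plan's own figures.** 885 cannot be reproduced, because none of the inputs to a sample-size formula is given. 650 is consistent as a sum: 120 + 530 = 650, and 60 + 60 + 265 + 265 = 650.

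**2. The gap.** 885 - 650 = 235; 650/885 = 0.734.

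**3. Does a stated rate link the totals directly?**
- 20% loss: 885 x 0.80 = 708; 650/0.80 = 812.5, so 813. Neither matches.
- 30% participation: 650/0.30 = 2,167 approached; 885/0.30 = 2,950 approached. Neither matches.
- Adding the Phase I (40) and usability (10) participants: 650 + 50 = 700. No match.

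Section 8C places randomisation after the Baseline Questionnaire and states no loss in between, so attrition there cannot account for the 235.

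**4. A possible origin.** 885 x 0.30 = 265.5, against 265 per ethnic group in the PGT-SC arm. Two such groups plus the controls give 2 x 265.5 + 120 = 651, against 650. This requires 885 to be the number approached in each ethnic group for the PGT-SC arm alone. On that reading it is not a total of any kind: 2 x 885 = 1,770 would be approached for that arm and 120/0.30 = 400 for the controls, 2,170 in all.

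**5. Illustration of what each total could detect.** Assumed, not in the documents: two-sided 5%, 80% power, no multiplicity adjustment, no adjustment for baseline.

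Arms: difference in SD = (1.960 + 0.842) x sqrt(1/n1 + 1/n2).
- 120 vs 530: 2.802 x sqrt(0.01022) = 0.28.
- 96 vs 424 (20% lost in each arm): 2.802 x sqrt(0.01278) = 0.32.
- 885 at the same allocation: 0.24, or 0.27 after 20% loss.

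Reach by ethnicity, n per group, overall rate c, rates c - d/2 and c + d/2: d solves d x sqrt(n) = 1.960 x sqrt(2c(1 - c)) + 0.842 x sqrt(p1(1 - p1) + p2(1 - p2)). The values of c are 30% and 50%, the two rates that section 8D gives for registering a decision.
- 265 vs 265 (PGT-SC arm only): 11.1 points at c = 30% (24.4% vs 35.6%); 12.1 points at c = 50%.
- 325 vs 325 (controls counted once they are offered testing): about 10 points at 30%; 11.0 points at 50%.
- 885 at the same allocation, 361 vs 361 (PGT-SC arm only): 9.5 and 10.4 points.

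**The case against.** The best defence is that 885 is a count of people approached. It follows directly on the 30% rate, and the arithmetic in step 4 lands within one of 650. The word participants does not by itself rule this out, because the opening of section 8C also applies it to people who have been approached but have not yet consented. This stands as a possible origin. It does not resolve the conflict: section 8C presents 885 as a total that the outcomes require, section 22 as a number to recruit, and neither mentions a count per ethnic group.

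Second, section 6 refers to a Study Flow figure, which could not be read here. A bridge inside it cannot be excluded. It would not remove the need to correct sections 8C and 22 if they do not mean what they say.

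Third, 885 is attributed to sample size estimates, so it would be unfair to say that neither total has any claimed basis. That is right: the basis for 885 is asserted without being shown, and only 650 lacks even an assertion.

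Fourth, the allocation, the table and the arm sizes all agree at 650, and the detectable differences at 650 and 885 are not far apart. This is also fair. It suggests that 650 is the operating number and limits how much should be read into the gap.

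**Conclusion.** The text is wrong as written: it declares 885 necessary and delivers 650, a difference of 235. No stated step connects the two, subject to the unread figure and to the possible origin in step 4.

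A reader might infer that the trial is underpowered, or short by 235 people. The documents do not support that. They give no effect size or power against which 650 could be judged, and the conflict does not show which total is right. Under the assumptions of step 5, going from 650 to 885 would move the arm comparison only from 0.32 to 0.27 SD after loss, and reach by about 1.6 to 1.7 points on the PGT-SC arm alone. Those figures are illustrations. They depend on choices that the protocol leaves open: alpha and power, multiplicity, baseline adjustment, how missing follow-up is treated, and whether controls count toward reach.

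The comparison of testers with controls is not put into figures here, because the expected number of testers depends on which passage is used. Section 6 says "we anticipate 30-50 percent will accept an invitation for testing". Section 8D expects at least 30% to register a decision of either kind, and up to half of those who consider testing to return a sample.

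**What to change.** Reconcile sections 6, 8C and 22 to one Phase II total, check it against the Study Flow figure, and say where 885 came from. It should not simply be deleted.

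- **If 650 is the operating number:** replace the section 8C sentence that calls 885 necessary, change 885 to 650 in section 22, and add the sponsor's own statement of what 650 can detect for the randomised-arm comparison and for reach by ethnicity. That statement should give alpha, power, loss allowance, the uptake reading used (section 6 or section 8D) and whether controls count toward reach. The figures in step 5 are not a substitute for it.
- **If 885 meant people approached:** say so, state the unit (per ethnic group or overall), and correct the wording in sections 8C and 22 that presents them as participants to be recruited. The detectable-difference statement for 650 is still needed.
- **If 885 participants are really required:** revise the arm sizes and table in sections 6 and 8 to sum to 885, and show the calculation.

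The first two routes cost wording and a short power statement, with no extra enrolment; the protocol can then no longer say that its required size is 885. The third costs 235 more participants, or about 235/0.30 = 783 more people approached.

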- 1) **Personalized Genomic Testing for Skin Cancer – Maximizing Utility and Reach – 05/16/17**
- (v. 10)
- 2) **IRB Review History N/A**
- 3) **Objectives**

This study will have two phases, with an added usability test after Phase I and before Phase 2. Phase 1: Cognitive Interviews in Spanish.

Phase 2: Personalized Genomic Testing for Skin Cancer (PGT-SC).

The overarching goal of this study is to learn more about how to maximize the availability, comprehension and appropriate uptake of personalized genomics among different populations in New Mexico. The proposed study has been funded as an R01 by NCI for three years.

Aim I: To examine the personal utility (that is, how does personal genomic testing help the individual) of Personal Genomic Testing for Skin Cancer (PGT-SC) in terms of short-term (three months after testing) sun protection, skin screening (i.e., behaviors), communication, melanoma threat and control beliefs (i.e., putative mediators of behavior change). Guided by Protection Motivation Theory (Robberson and Rogers, 1998), **we hypothesize that behaviors and putative mediators will be higher in those who test, compared to those who decline testing or wait-list controls.**

Aim Ia. An important challenge of personal genomics involves the potential for those who receive “negative” genetic feedback to increase risky behaviors (McBride et al., 2010). To examine this potential unintended consequence of testing, we will conduct a subgroup analysis among those who receive average risk PGT-SC findings, examining sun protection at three months as the outcome. Predictors will include baseline skin cancer threat and control beliefs, skin cancer risk factors, and demographics. These findings will be used in future studies to develop messages for groups that receive average risk feedback, which accounts for large segments of those tested for moderate risk susceptibility factors across many diseases.

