Cognitive interviews to ensure high comprehensibility and acceptability of the translations will be conducted by [name] and [name].

The Department of Psychiatry & Behavioral Sciences at MSKCC will conduct data analysis on de-identified data.

11) Study Methods

*The timeline above gives very detailed information about study methods.

Subjects will be approached at their Clinic and asked if they are interested in participating. Individuals accompanying Clinic patients and who attend another UNM Clinic are eligible to participate.

They will then discuss the study with the bilingual interviewer and, if they are eligible agree and sign informed consent. All baseline surveys will then be completed with the PA in the clinic.

Identifiers will be collected and remain at UNM for mailing and follow-up. Subjects will then be de-identified at the end of the study (after 3 years).

Subjects will receive compensation for participation. ALL consented subjects will receive a \$15 Target Gift card after completion of the Baseline Questionnaire; those in the randomized to the wait list control Group 1 will receive compensation for the baseline survey and the three-month survey. Those randomized to Group 2, the PGT-SC arm will then be given information modules through the internet (or on paper if they prefer). They will be asked if they would like to participate in genetic testing for MC1R. Those randomized to receive PGT-SC who complete the online educational modules will be compensated \$5 Target Gift card per educational module, with a maximum of \$15 possible.

Additionally, among those who elect genetic testing, we will assess distress levels two weeks after the PGT -SC genetic results have been received, and will compensate participants for their time with a \$5 target Gift card. All participants who completed Baseline Assessments (whether tested or not) will be contacted for the final assessment by telephone approximately three months after recruitment.

Participants who complete the three-month outcome assessment will receive a \$15 Target Gift card. This level of compensation is reasonable for the level of effort required for subjects.

12) Data and Specimen Banking

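### The three-month outcome call is timed from testing in section 8E and from recruitment in section 11, and the 8E rule gives no call date for controls or other non-testers

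*Combined protocol and SAP*

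**What the plan says.** Four places in the combined protocol and SAP bear on when the three-month outcome is measured.

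- **Section 8, E (Three-month follow-up).** All who completed baseline, regardless of testing, "will be contacted for assessment by telephone three months after PGT-SC testing".
- **Section 11 (Study Methods).** The same group "will be contacted for the final assessment by telephone approximately three months after recruitment". The section opens by referring back to section 8: "The timeline above gives very detailed information about study methods".
- **Section 3, Aim I.** Personal utility is described "in terms of short-term (three months after testing) sun protection" and the other outcomes. The hypothesis is that outcomes "will be higher in those who test, compared to those who decline testing or wait-list controls".
- **Section 9 (Study Endpoints).** "Primary endpoints are based on the 3-month follow up questionnaires". The endpoint is again worded as three months after testing.

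Section 8, F adds that the 120 controls "will receive an offer for PGT-SC directly after the three-month follow-up assessments"; section 6 agrees. Section 8, G estimates three months in the study per person.

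**The concern.** Two sentences, nearly the same apart from the starting date, put one call on two clocks. Section 11 cannot be read as simply overriding 8E, because it sends the reader back to the timeline that contains 8E.

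The 8E clock also needs a test date, and many of the people it covers have none. For controls it is circular: the call would be dated from a test that is offered only after the call. Non-testers in the PGT-SC arm never get a date. No substitute starting date is given for either group.

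The call date fixes when the Aim I behavioural and belief outcomes are measured. If staff filled the gap by calling testers three months after testing and everyone else three months after recruitment, testers would have had longer since baseline than their comparators. An outcome such as having had a health provider skin examination (no/yes) could then partly reflect extra elapsed time. No passage prescribes that mixed rule, so this is a risk and not a demonstrated bias.

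**Working it through.** The plan gives no figure of its own to reproduce here. The check compares the timing rules and then counts who has a usable date under each.

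**Inputs**

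- Arm sizes: 120 controls and 530 PGT-SC, 650 in total (sections 6 and 8C).
- Acceptance of testing: 30-50% (section 6).
- Controls offered testing only after the three-month questionnaire (sections 6 and 8F).
- Results within one month (section 8D), taken here as counted from sample return.
- Randomisation directly follows the baseline questionnaire (section 8C).

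**Step 1. Who has a start date under 8E**, counting everyone who accepts as tested:

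| | 30% accept | 50% accept |
|---|---|---|
| PGT-SC testers | 530 × 0.30 = 159 | 530 × 0.50 = 265 |
| PGT-SC non-testers | 530 − 159 = 371 (70%) | 530 − 265 = 265 (50%) |
| Controls with no test date | 120 | 120 |
| Total with no start date | 371 + 120 = 491 | 265 + 120 = 385 |
| Share of 650 | 75.5% | 59.2% |

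**Step 2. Sensitivity to the uptake figure.** Section 8D expects 30-50% to register a decision and up to 50% of those who consider testing to return a sample. If these are multiplied:

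- Testers: 530 × 0.30 × 0.50 = 79.5, to 530 × 0.50 × 0.50 = 132.5.
- No start date: 650 − 132.5 = 517.5 (79.6%), to 650 − 79.5 = 570.5 (87.8%).

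The range in step 1 is therefore the more favourable to the plan.

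**Step 3. What the section 11 clock implies for testers.** If a result takes the full month, time since result at the call is at most 3 − 1 = about 2 months. Time spent on the modules and the kit reduces it further, and the documents do not give that time. As an illustration, assume 0-8 weeks from recruitment to sample receipt, with three months as 13.05 weeks and one month as 4.35 weeks:

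- 0 weeks to sample, immediate result: 13.05 − 0 − 0 = about 13 weeks since result.
- 8 weeks to sample, full month for the result: 13.05 − 8 − 4.35 = 0.7 weeks since result.

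**Step 4. What the 8E clock implies for testers**, on the same assumptions:

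- Dated from the sample: 13.05 + 0 = about 13 weeks, to 13.05 + 8 = about 21 weeks after recruitment.
- Dated from the result: up to 13.05 + 8 + 4.35 = about 25 weeks after recruitment.

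The plan does not say whether testing means the sample, the assay or receipt of the result.

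**Step 5. Fit with the rest of the text.** Section 11 can be applied to everyone and fits the three months in study in 8G, but not the endpoint wording in Aim I and section 9. The 8E rule fits that endpoint wording but cannot be applied to most participants. Neither clock agrees with the whole document.

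**The case against.** The best reply is that section 11 already supplies a workable rule. It covers the same people, it can be applied to all of them, and if it is used throughout, no timing difference between groups arises from this source. The phrase about three months after testing could be a loose gloss on short-term, and section 11 itself says approximately. That limits the harm but does not settle which rule governs, since Aim I, 8E and section 9 all say after testing.

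Several narrower points stand:

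- The 59-76% counts people without a date under a literal 8E. It does not measure bias.
- The three-month estimate in 8G is weak support for either clock, because controls who go on to test stay in longer.
- The section 9 table restricts part of the belief and communication assessment at three months (for beliefs, to risk perception). The items that remain are still dated by this call.
- Differential reach, also primary, is measured by registration of a test decision and is unaffected.
- The study flow figure, questionnaires, appointment card and introduction letters are not in the supplied text and may carry call timing. They would not remove the conflicting sentences.
- A matched or surrogate date for non-testers could preserve the endpoint as worded. It would need a new assignment rule, whereas a randomisation date exists for everyone.

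**Conclusion.** The concern holds and should be fixed. Sections 8E and 11 give incompatible dates for the call that supplies the Aim I primary outcomes, and the 8E rule has no start date for 385-491 of 650 participants (59-76%). That range rests on the planned arm sizes, on 30-50% acceptance, and on treating every acceptor as tested; a stricter reading of uptake raises it to 80-88%.

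Under section 11 the groups are on the same clock, but a tester whose result takes the full month is at most about two months past it, so the endpoint as worded in Aim I and section 9 would not be what is measured. How far the two clocks diverge, and any bias from mixing them, cannot be derived, because the time from recruitment to testing is not given.

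**What to change.** Reconcile section 3 (Aim I), section 8E, section 9 and section 11 to one rule: the outcome call at the same fixed interval and window from randomisation, in both arms and in all uptake groups. This is in effect section 11's recruitment clock. Reword the endpoint in Aim I and section 9 to match, and report the distribution of testers' time since result at the call. Where a result arrives close to or after the call, that distribution will show it; this situation already exists under section 11, and the analysis should say how such participants are classified.

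The cost is wording in four places, a call calendar keyed to the randomisation date, and that short statement on classification. No new procedure or data item is needed, because the date results are mailed must already be tracked for the two-week call in section 8D. The price is that the Aim I endpoint is no longer three months after testing: testers' time since result will vary and will be shorter than three months.
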